8. SAFETY ANALYSES

The safety analyses will be based on the “Safety” population, unless otherwise specified. Outputs will be presented separately for study part A and study part B.

8.1. Overview of Planned Adverse Events Analyses

Adverse Events will be coded using Medical Dictionary for Regulatory Activities (MedDRA) central coding dictionary and summarized by dose group.

Counting of AEs will be based on the number of subjects – not the number of AEs. For example if a subject experiences the same AE (i.e. same preferred term) more than once, they are counted only once under the count for the preferred term. If a subject experiences more than one AE in a particular SOC, they will only be included once in the count for the SOC, but will appear in the count for each appropriate preferred term within the SOC. Therefore, the sum of the numbers of subjects with each preferred term event within a SOC may exceed the total number of subjects with at least one event. For the summary of AEs by maximum intensity, subjects who experience the same event several times with different intensity will only be counted once with the maximum intensity.

[Table 6](#) provides an overview of the planned analyses, with further details of data displays being presented in [Appendix 10: List of Data Displays](#).

Table 6 Overview of Planned Adverse Event Analyses

Endpoint / Parameter/ Display Type	Absolute		
	Summary		Individual
	T	F	L
Adverse Events (AEs)			
All AE's	Y		Y
Serious AE's	Y		Y
Drug Related AEs	Y		Y
AE's leading to withdrawal	Y		Y
Common (>=5% in any treatment group) Non-serious AEs by SOC and PT – number of subjects and occurrences	Y		
Serious Adverse Events by System Organ Class and Preferred Term (Number of Subjects and Occurrences)	Y		
Relationship Between System Organ Class And Verbatim Text			Y
Subject Numbers for Individual Adverse Events			Y

NOTES:

- T = Table, F = Figures, L = Listings, Y = Yes display generated
- Summary = Represents TF related to any summaries (i.e. descriptive statistics) of the observed raw data.
- Individual = Represents FL related to any displays of individual subject observed raw data.

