4. STUDY DESIGN

4.1. Part A (Single Dose)

Figure 1 Part A Schematic

★ Dose escalation meeting

- o One of the dosing periods will be a food effect group – the dose will be determined based on data from previous cohorts
- o There will be a 2 week washout between doses initially but the washout period may be modified depending on emerging data from previous cohorts.
- o Cohorts 1 and 2 will be dosed sequentially. If it is considered desirable to dose Cohorts 1 and 2 in an overlapping/interlocking fashion, approval will be sought from the Regulatory Agency first.

Up to two cohorts will be included in the single dose part (Part A). Each cohort will participate in up to 4 treatment (dosing) periods (including a food effect treatment period). Initially, there will be a 14 day wash out period for individual subjects between each dose level which is considered sufficient in light of the predicted half-life of GSK3036656 [on average, approximately 30 hours (range: 12 to 72 hours) based on the various preclinical extrapolation methods], however this may be revised once relevant PK data is obtained. Nine subjects per cohort will be enrolled and randomised to ensure adequate safety, tolerability and PK information is gained and a balanced randomisation is achieved across all treatment (dosing) periods.

During each treatment (dosing) period, GSK3036656 will be administered to 6 subjects and placebo will be administered to 3 subjects. As this is a FTIH study, each treatment (dosing) period will be staggered over 2 days. On Day 1 of each dose level, one subject will receive GSK3036656 and one subject will receive placebo. The remaining subjects within the dosing group will be dosed one day later provided satisfactory safety and tolerability is demonstrated for the subjects dosed on Day 1. A treatment (dosing) period does not have to be staggered if the dose administered is equal to or lower than a dose that has been already tested and found to be safe and well tolerated.

Subjects will attend the unit on Day -1 for assessments and a meal. The subjects will then fast overnight (at least 8 hours) and be dosed the following morning (Day 1). Dosing with food may also be done in Part A once results from the food effect analysis are available. Dividing the total dose for the treatment (dosing) period into 2 or 3 smaller doses administered within 24 hours may also be done. The decision to divide the total dose into

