4.4. Design Justification

The FTIH study with GSK3036656 will evaluate the safety of the compound in healthy volunteers in order to avoid confounding factors resulting from the disease or concomitant drugs in patients with TB that may hinder the proper evaluation of safety. Also, ethical considerations dictate exploration of safety and tolerability in healthy volunteers first as patients with TB may be more vulnerable to side effects caused by the compound.

A cross-over design is preferred for Part A as it would allow assessment of safety and PK in the same individual thus reducing the influence of inter-individual variability.

Based on the physicochemical properties of GSK3036656, no significant food effect is predicted. Nevertheless, the study will investigate the possibility of food effect in order to provide guidance for dosing in future studies. If the FTIH study with GSK3036656 is successful, the next study in humans is expected to be an efficacy study in patients with TB where the compound is dosed for up to 2 weeks. Therefore, the proposed dosing for up to 14 days in Part B of the FTIH study is an appropriate first step in evaluating the safety of GSK3036656.

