10.4 Appendix 4: Data Display Standards & Handling Conventions

10.4.1 Study Treatment & Display Descriptors:

Treatment Group Descriptions			
RandAll NG		Data Displays for Reporting	
Part	Code	Description	Description ^[1]
A	P	Placebo	Placebo
A	D1	GSK3036656 Dose 1	Dose X mg
A	D2	GSK3036656 Dose 2	Dose X mg
A	D3	GSK3036656 Dose 3	Dose X mg
A	D4	GSK3036656 Dose 4	Dose X mg
A	D5	GSK3036656 Dose 5	Dose X mg
A	D6	GSK3036656 Dose 6	Dose X mg
A	D7	GSK3036656 Dose 7	Dose X mg
A	D8	GSK3036656 Dose 8	Dose X mg
B	P	Placebo	Placebo
B	R1	GSK3036656 Repeat Dose 1	Repeat Dose X mg
B	R2	GSK3036656 Repeat Dose 2	Repeat Dose X mg
B	R3	GSK3036656 Repeat Dose 3	Repeat Dose X mg
B	R4	GSK3036656 Repeat Dose 4	Repeat Dose X mg

NOTES:

The decision to proceed to each subsequent dose level will be made by the Dose Escalation Committee (DEC)

Note, in tables, figures and listings, treatments should be presented with placebo first, then in order of increasing dose within each study part.

1. 'Dose X' to be replaced by actual dose.

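### Part A adverse event tables count subjects once in a pooled placebo column that, at the full schedule, averages at least 1.33 administrations per subject, which modestly overstates the placebo percentage against single-period dose columns

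*SAP*

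**What the plan says.** SAP 8.1 sets the counting unit: "Counting of AEs will be based on the number of subjects – not the number of AEs". A subject is counted once per preferred term and once per system organ class. Adverse events are coded with the MedDRA "central coding dictionary and summarized by dose group", and SAP 8 splits outputs by study part only.

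SAP 10.4.1 lists the Part A treatment descriptors: one placebo code (P) and eight dose codes (D1 to D8). Its note on displays says that "treatments should be presented with placebo first, then in order of increasing dose within each study part". Neither section splits placebo by cohort, period or fed/fasted state, and neither gives a denominator based on administrations.

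On design, Protocol 4.4 says "A cross-over design is preferred for Part A". Protocol 4.1 allows up to two cohorts and up to four periods per cohort, one of them for the food effect. It adds: "Nine subjects per cohort will be enrolled and randomised" and "During each treatment (dosing) period, GSK3036656 will be administered to 6 subjects and placebo will be administered to 3 subjects".

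**The concern.** In a cross-over, one subject can supply several placebo periods. If these are pooled into one column and the subject is counted once, that subject has several chances of an event but adds only one to the denominator. A dose given in a single period has one administration per subject, so the two percentages rest on different amounts of observation.

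Safety and tolerability is the first primary objective, and the adverse event tables are its main summary. An overstated placebo percentage makes a single-period dose look somewhat better tolerated by comparison. Placebo taken with the high-fat meal would also sit in the comparator for fasted doses.

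A related gap is that SAP 10.3.1 classifies events only against study treatment start and stop. It does not say to which cross-over period an event belongs.

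**Working it through.** **Inputs from the documents.** 9 subjects per cohort; 6 active and 3 placebo per period; up to 4 periods; up to 2 cohorts (Protocol 4.1). The planned Part A sample size is 18 (Protocol 10.2), which 2 × 9 = 18 reproduces.

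**Is four periods the planning case?** The documents set it as a maximum, but two features match it. D1 to D8 equals 2 cohorts × 4 periods. The stated Part A duration of about 12 weeks equals 28 days of screening + 3 × 14 days of washout + 14 days of follow-up = 84 days.

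**Placebo administrations per subject.**
- Full schedule: 2 × 4 × 3 = 24 administrations over at most 18 subjects, so the mean is at least 24/18 = 1.33.
- Most even layout in a cohort: 12 administrations over 9 subjects, so 6 subjects take placebo once and 3 take it twice.
- Four periods in one cohort and three in the other: 21/18 = 1.17.
- Three periods in each cohort: 18/18 = 1.00.
- Full schedule with one, two or three replacements per cohort: the minimum falls to 12/10 = 1.20, 12/11 = 1.09 or 12/12 = 1.00.
- A single-period dose column: 6/6 = 1.00.

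**Expected placebo percentage.** The documents give no event rate, so p, the chance of the event per administration, is assumed and taken as equal in every period. With independent events and the most even layout, the expected percentage is [6p + 3(1 − (1 − p)²)]/9.

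| Assumed p | Placebo column expects | Ratio to p | Excess (points) |
|---|---|---|---|
| 5% | 6.6% | 1.32 | 1.6 |
| 10% | 13.0% | 1.30 | 3.0 |
| 20% | 25.3% | 1.27 | 5.3 |
| 30% | 37.0% | 1.23 | 7.0 |
| 50% | 58.3% | 1.17 | 8.3 |

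For p = 10%: (6 × 0.10 + 3 × 0.19)/9 = 1.17/9 = 13.0%.

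**Dropping independence.** If a subject's two placebo periods have correlation ρ, the chance of at least one event is p + p(1 − p)(1 − ρ). The excess in the even layout is then p(1 − p)(1 − ρ)/3. At p = 10% this is 3.0 points for ρ = 0, 1.5 points for ρ = 0.5, and nil for ρ = 1. It is never negative, because the chance of at least one event in two periods cannot be below p.

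**Fed and fasted at the same dose.** SAP 10.4.1 labels reported columns by the actual dose in mg, and Protocol 4.1.1 has the fed period reuse a dose already given fasted in the same cohort. If both share one label, that column holds 12 administrations. With 6 of 9 subjects active in each period, at least 6 + 6 − 9 = 3 are active in both, so the column has 6 to 9 subjects and a mean of 1.33 to 2.0. At p = 10% with independent events it expects 13.0% with 9 subjects and 1 − 0.9² = 19.0% with 6, against 13.0% for placebo in the even layout.

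**The case against.** The best case against acting has four parts.

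**The effect is small.** Over 18 placebo subjects, the even-layout excess is 18 × 0.030 = 0.5 subject at p = 10% and 18 × 0.053 = 1.0 subject at p = 20%. One event in a six-subject dose column moves that column by 16.7 points. Positive within-subject correlation shrinks the excess further. This stands, and it makes the point modest.

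**No dosing decision depends on it.** Protocol 5.5 compares the active subgroup at the last dose level with the placebo subgroup within a group or cohort, and Protocol 5.6 counts events in active subjects only. The affected tables are final and descriptive, and no hypothesis is tested. A reader might infer that the pooled column could hide a signal during escalation; the documents do not support that.

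**Other displays help.** Of the Part A tables, 3.9 (common non-serious events) and 3.11 (serious events) also give occurrences, and adverse event listings are planned. However, Tables 3.1, 3.3, 3.5 and 3.7 (all, serious, drug-related and leading to withdrawal) are not labelled as giving occurrences.

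**The reading is partly an inference.** Pooling follows from the single code P and is not put in words. The denominator is left to sponsor standard shells that are not in the documents. This is fair, but one placebo column counted by subject is the natural reading, and no text sets it aside.

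**Conclusion.** The point holds in a limited form. At the full 2 × 4 schedule without replacements, the plan as written would modestly overstate the Part A placebo percentage relative to single-period dose columns: 13.0% instead of 10%, or 25.3% instead of 20%. These figures assume the most even layout, independent events and an assumed p. The excess is smaller with positive within-subject correlation and nil with three balanced periods.

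Three stronger readings are tempting and are not supported:
- That every placebo subject has at least 1.33 administrations. The figure is a minimum mean at the full schedule; in the even layout 6 of 9 subjects per cohort take placebo exactly once.
- That the bias always favours the active doses. If fed and fasted periods share one mg label, that active column also holds more than one administration per subject, and the direction is not fixed for it.
- That the inflation reaches 1.5 to 1.6 times. That needs placebo to be drawn independently in each period (15.8% at p = 10%, 30.1% at p = 20%), which conflicts with the balanced randomisation across periods that Protocol 4.1 intends.

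**What to change.** In SAP 8.1 and 10.4.1, for the Part A adverse event tables:
1. Assign each adverse event to the period of the most recent dose.
2. Show the number of administrations (subject-periods) in each column, up to 24 for placebo in total, and give percentages on that denominator alongside the number of distinct subjects.
3. Give fed dosing, active and placebo, its own columns separate from fasted.

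With administrations as the denominator, the expected placebo percentage returns to p, and columns compare like with like whether a dose was given in one period or more.

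The cost is SAP wording and a denominator change in the Part A tables, using data already collected. The downside is that subject-periods from one person are correlated, so the percentages are not based on independent units. That is acceptable in a descriptive table, and the count of distinct subjects keeps it visible.

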8.2. Overview of Planned Clinical Laboratory Analyses

Table 7 provides an overview of the planned analyses, with further details of data displays being presented in [Appendix 10: List of Data Displays](#).

Table 7 Overview of Planned Clinical Laboratory Analyses

Endpoint / Parameter/ Display Type	Absolute			Change from BL		
	Summary		Individual	Summary		Individual
	T	F	L	T	F	L
Chemistry						
Clinical Chemistry	Y		Y	Y		Y
Haematology						
Haematology	Y		Y	Y		Y
Urinalysis						
Urinalysis	Y		Y			

NOTES:

- T = Table, F = Figures, L = Listings, Y = Yes display generated
- Summary = Represents TFL related to any summaries (i.e. descriptive statistics) of the observed raw data.
- Individual = Represents FL related to any displays of individual subject observed raw data.

8.3. Overview of Planned Other Safety Analyses

Table 8 provides an overview of the planned analyses, with further details of data displays being presented in [Appendix 10: List of Data Displays](#).

Table 8 Overview of Planned Other Safety Analyses

Endpoint / Parameter/ Display Type	Absolute			Change from BL		
	Summary		Individual	Summary		Individual
	T	F	L	T	F	L
ECG						
ECG Findings	Y		Y			
ECG Values	Y		Y	Y		Y
ECG Values Outside the PCI Range			Y			
Telemetry			Y			
Vital Signs						
Vitals Values	Y		Y	Y		Y
Vital Signs Measurements Outside the PCI Range			Y			

NOTES:

- T = Table, F = Figures, L = Listings, Y = Yes display generated, PCI = Potential Clinical Importance
- Summary = Represents TFL related to any summaries (i.e. descriptive statistics) of the observed raw data.
- Individual = Represents FL related to any displays of individual subject observed raw data.

10. APPENDICES

Section	Appendix
RAP Section 4 : Analysis Populations	
Section 10.1	Appendix 1: Protocol Deviation Management
RAP Section 5 : General Considerations for Data Analyses & Data Handling Conventions	
Section 10.2	Appendix 2: Time and Events
Section 10.3	Appendix 3: Treatment States & Phases
Section 10.4	Appendix 4: Data Display Standards & Handling Conventions 
 • Study Treatment & Sub-group Display Descriptors • Baseline Definitions & Derivations • Reporting Process & Standards
Section 10.5	Appendix 5: Derived and Transformed Data 
 • General • Study Population • Safety • Pharmacokinetic
Section 10.6	Appendix 6: Premature Withdrawals & Handling of Missing Data 
 • Premature Withdrawals • Handling of Missing Data 
 ○ Handling of Missing Dates ○ Handling of Partial Dates
Section 10.7	Appendix 7: Values of Potential Clinical Importance 
 • Laboratory Values • ECG • Vital Signs
Section 10.8	Appendix 8: Model Checking and Diagnostics for Statistical Analyses
Other RAP Appendices	
Section 10.9	Appendix 9 : Abbreviations & Trade Marks
Section 10.10	Appendix 10: List of Data Displays
Section 10.11	Appendix 11: Example Mock Shells for Data Displays

10.1 Appendix 1: Protocol Deviation Management

There are no pre-defined categories leading to exclusion from the PK population but all protocol deviations will be reviewed on a case-by-case basis.

No subjects will be excluded from the safety population.

10.2 Appendix 2: Time & Events

10.2.1 Protocol Defined Time & Events

Part A

Part A	Screening	Day					Follow-up
		-1	1	2	3	4	
Days	-28 to -2						15
Informed consent	X						
Inclusion/exclusion criteria ¹	X		X				
Medical/surgical history	X						X
Admission			X				
Inpatient stay			<—————→				
Dose of GSK3036656 ²				X			
Echocardiogram ³	X						X
Discharge						X	X
Outpatient visit ⁴	X	X					X
Safety assessments							
Physical examination ⁵	X		X		X		X X
Height & weight ⁵	X						
Vital signs ⁶	X		X	X	X	X	X X
12-lead ECG ⁷	X			X	X	X	X X
Holter monitoring ⁸	<—————→						
Telemetry ⁹				<—————→			
Clinical laboratory assessments							
Screening tests (incl blood FSH & estradiol for female subjects only)	X						
Haematology, biochemistry and urinalysis ¹⁰	X		X		X		X X
Pregnancy test (female only) ¹¹	X		X				
Urine drug screen, alcohol & smoking breath tests	X		X				
PK samples							
Blood for PK GSK3036656 ¹²				X	X	X	X
Total urine collection ¹³				X	X	X	X
Concomitant therapy review ¹⁴	<—————→						
Adverse events ¹⁴	<—————→						

1 Inclusion/exclusion criteria will only be assessed at Day-1 of the first period.

2 In the event of a divided dose, alterations to event time points may be communicated in a file note. For the food effect assessment, the selected dose will be given with a high fat meal.

3 Echocardiograms may be done at a separate screening visit.

4 When there is Holter monitoring at screening, subjects will return after 24 h to have the Holter removed.

5 Brief physical examination will be done at admission (Day-1) and in the morning on Days 2 and 4 in each

treatment session. Full physical examination will be done at screening and follow-up (to include height and weight at screening only).

- 6 Blood pressure, heart rate, tympanic temperature and respiratory rate. Vital signs will be recorded: at pre-dose and at 0.5, 1, 2, 3, 4, 6, 12, 24, 48 and 72 h after dosing on Day 1.
- 7 ECGs will be recorded at pre-dose and at 0.5, 1, 2, 3, 4, 6, 12, 24, 48 and 72 h after dosing on Day 1. Triplicate measurements (about 2-5 mins apart) will be taken at pre-dose; single measurements will be taken at all other time points.
- 8 24 h Holter monitoring at screening only.
- 9 Telemetry will be recorded from -1 h pre-dose until 24 h post-dose
- 10 Haematology, clinical chemistry, and urinalysis will be done at Day-1 and at 24 and 72 h post-dose.
- 11 Pregnancy testing of female subjects only. At screening pregnancy test will be done using the blood sample; urine pregnancy test will be done on admission.
- 12 Blood samples for assay of GSK3036656 will be taken: at pre-dose and at 0.25, 0.5, 0.75, 1, 1.5, 2, 3, 4, 6, 8, 12, 15, 24, 36, 48 and 72 h after dosing on Day 1.
- 13 Total urine collections for GSK3036656 will be performed at the following time points: pre-dose and 0-6, 6-12, 12-24, 24-48 and 48-72 h after dosing on Day 1.
- 14 AEs and concomitant medications will be recorded collected from the start of informed consent until the follow-up contact.

Part B

Part B	Screening	Day																	Follow-up	
		-1	1	2	3	4	5	6	7	8	9	10	11	12	13	14	15	16	17	
Days	-28 to -2																			
Informed consent	X																			
Inclusion/exclusion criteria	X		X																	
Medical/surgical history	X																		X	
Admission			X																	
Inpatient stay				←	→															
Dose of GSK3036656 ¹				X	X	X	X	X	X	X	X	X	X	X	X	X	X			
Echocardiogram ²	X																		X	
Discharge																		X		X
Outpatient visit ³	X	X																X	X	X
Safety assessments																				
Physical examination ⁴	X		X		X		X		X		X		X		X		X		X	
Height & weight ⁴	X																			
Vital signs ⁵	X		X	X	X	X	X	X	X	X	X	X	X	X	X	X	X	X	X	
12-lead ECG ⁶	X			X	X	X	X		X			X				X			X	
Holter monitoring ⁷		←	→																	
Telemetry ⁸				←	→															
Clinical laboratory assessments																				
Screening tests (incl blood FSH & estradiol for female subjects only)	X																			
Haematology, biochemistry and urinalysis ⁹	X		X			X		X		X		X		X		X		X		X
Serum pregnancy test (female only) ¹⁰	X		X																	
Urine drug screen, alcohol & smoking breath tests	X		X																	
PK samples																				
Blood for PK GSK3036656 ¹¹				X	X	X	X								X	X	X	X	X	
Total urine collection ¹²				X	X										X	X				
Concomitant therapy review ¹³		←	→																	
Adverse events ¹³		←	→																	

- 1 Dosing of GSK3036656 should be at approximately the same time each day. In the event of a divided dose, alterations to event time points may be communicated in a file note.
- 2 Echocardiograms may be done at a separate screening visit.
- 3 When there is Holter monitoring at screening, subjects will return after 24 h to have the Holter removed.
- 4 Brief physical examination will be done on Days-1, 2, 4, 6, 10, and 15. Full physical examination will be done at screening and follow-up (to include height and weight at screening only).
- 5 Blood pressure, heart rate, tympanic temperature and respiratory rate. Vital signs will be recorded: at pre-dose and at 0.5, 1, 2, 3, 4, 6, 12, 24, 48 and 72 h after dosing on Days 1 and 14; and at pre-dose on Days 5-13.
- 6 ECGs will be recorded at pre-dose and at 0.5, 1, 2, 3, 4, 6, 12, 24, 48 and 72 h after dosing on Days 1 and 14; and at pre-dose on Days 6 and 10. Triplicate measurements (about 2-5 mins apart) will be taken at pre-dose; single measurements will be taken at all other time points.
- 7 24 h Holter monitoring at screening only.
- 8 Telemetry will be recorded from -1 h pre-dose until 24 h post-dose on Day 1.
- 9 Haematology, clinical chemistry and urinalysis will be done on Day-1 and in the morning (pre-dose if feasible) on Days, 4, 6, 10, and 15.
- 10 Pregnancy testing of female subjects only. At screening pregnancy test will be done using the blood sample; urine pregnancy test will be done on Day-1.
- 11 Blood samples for assay of GSK3036656 will be taken: at pre-dose and at 0.25, 0.5, 0.75, 1, 1.5, 2, 3, 4, 6, 8, 12, 15, 24, 36, 48 and 72 h after dosing on Day 1; and at pre-dose and at 0.25, 0.5, 0.75, 1, 1.5, 2, 3, 4, 6, 8, 12, 15, 24, 36, 48 and 72 h after dosing on Day 14. PK samples will also be taken pre-dose on Days 12 and 13.
- 12 Total urine collections for GSK3036656 will be performed at the following time points: pre-dose and 0-6, 6-12 and 12-24 h after dosing on Days 1 and 14.
- 13 AEs and concomitant medications will be recorded collected from the start of informed consent until the follow-up contact.

